4.7.1.3. Diabetes Treatment Satisfaction Questionnaire

Descriptive summaries will be provided at baseline (DTSQs only),observed endpoint, and endpoint including last observation carried forward excluding baseline observations (DTSQc only) for the perceived hyperglycemia item, perceived hypoglycemia item, and 6-item overall satisfaction score. The DTSQc score at Week 40, with and without LOCF, will be analyzed using an ANCOVA model with model terms of treatment, baseline HbA1c ($\leq 8.0\%$, $>8.0\%$ [≤ 64 , >64 mmol/mol]), and SGLT-2i use (Yes or No) as fixed effects, and baseline DTSQs score as a covariate. The analyses will be conducted for the perceived hyperglycemia item, perceived hypoglycemia item, and 6-item overall satisfaction score

4.7.1.4. EQ-5D-5L

A descriptive frequency table of individual items in EQ-5D-5L questionnaire will present baseline, observed endpoint, and endpoint including last observation carried forward (LOCF, exclude baseline observation) values as separate summaries. The changes from baseline to Week 40, with and without LOCF of the index and visual analog scale (VAS) scores will be analyzed using an ANCOVA model with model terms of treatment, baseline HbA1c ($\leq 8.0\%$, $>8.0\%$ [≤ 64 , >64 mmol/mol]) and SGLT-2i use (Yes or No) as fixed effects, and corresponding baseline EQ-5D-5L score as a covariate. The EQ-5D-5L health states, defined by the EQ-5D-5L descriptive system, may be converted into a single summary index by applying a formula (UK or China) that essentially attaches values (also called weights) to each of the levels in each dimension (EuroQol Group 2019).

4.7.2. Subgroup Analyses

Subgroup analyses of the primary endpoint, change from baseline in HbA1c, at week 40, will be made based on the efficacy estimand using the EAS to assess consistency of the intervention effect across the following subgroups:

- Age group: <65 years vs ≥ 65 years
- Sex: female vs male
- Duration of diabetes: (≤ 5 , >5 to ≤ 10 , >10 years)
- Duration of diabetes ($<\text{median}$, $\geq\text{median}$)
- Baseline BMI (<24 , ≥ 24 to <28 , $\geq 28/\text{kg}/\text{m}^2$),
- Concomitant OAM (no OAM, only metformin, metformin+SGLT-2i)
- Baseline HbA1c ($\leq 8.0\%$, $>8.0\%$)
- eGFR (<90 , ≥ 90 mL/min/1.73m 2)

4.7.2.1. Subgroup Analysis of Weight Change at Week 40

Subgroup analyses by the following baseline characteristics will be provided for weight change from baseline at Week 40 based on the efficacy estimand using EAS:

- Age group: <65 years vs \geq 65 years
- Sex: female vs male
- Duration of diabetes (<median, \geq median)
- Duration of diabetes: (\leq 5, >5 to \leq 10, >10 years)
- Baseline BMI (<24, \geq 24 to <28, \geq 28kg/m²)
- Concomitant OAM (no OAM, only metformin, metformin+SGLT-2i)
- eGFR (<90, \geq 90 mL/min/1.73m²)
- Baseline HbA1c (\leq 8.0%, >8.0%)

4.8. Interim Analyses

No interim analyses are planned for this study.

4.9. Important Protocol Deviations

Important protocol deviations are specified in the Trial Issues Management Plan (TIMP). A listing and a summary of important protocol deviations by treatment will be provided.

4.10. Changes to Protocol-Planned Analyses

NA

5. Sample Size Determination

Participants will be randomized in a 1:1:1:1 ratio to tirzepatide 5 mg, 10 mg, 15 mg, or placebo. The trial is powered to assess superiority of tirzepatide 10 mg and 15 mg, each tested in parallel, against placebo at a 2-sided significance level of 0.025, relative to the primary endpoint (mean change in HbA1c from baseline to 40 weeks), under the following assumptions: use of a 2-sample t-test utilizing HbA1c data collected before initiation of any rescue medication or premature treatment discontinuation with no more than 25% of participants initiating rescue medication or prematurely discontinuing treatment in each treatment group; 0.95% greater mean reduction in HbA1c from baseline for 10 and 15 mg tirzepatide compared with placebo; 1:1:1:1 randomization; and a common standard deviation (SD) of 1.3%. On the basis of these assumptions, a sample size of 256 participants is required to ensure at least 90% power to demonstrate that tirzepatide 10 mg and/or 15 mg are superior to placebo relative to the primary endpoint.

Assignment to treatment arms will be determined by a computer-generated random sequence using an interactive web response system (IWRS). Patients will be randomized in a 1:1:1:1 ratio to receive 5 mg tirzepatide, 10 mg tirzepatide, 15 mg tirzepatide, or placebo. The randomization will be stratified by baseline HbA1c concentration ($\leq 8.0\%$, $> 8.0\%$ [≤ 64 , > 64 mmol/mol]), and SGLT-2i use (Yes/No).

6. Supporting Documentation

6.1. Demographic and Baseline Characteristics

A listing of patient demographics will be provided. All demographic and baseline clinical characteristics will be summarized by study treatment for the patients in the modified intent-to-treat (mITT) population. Baseline demographic and clinical characteristics of special interest include but not limited to: age, gender, weight, BMI, HbA1c, fasting glucose, duration of T2DM, and estimated glomerular filtration rate (eGFR).

6.2. Treatment Compliance

Overall treatment compliance will be defined as taking at least 75% of the scheduled study drug or insulin glargine injections. Study drug compliance will be calculated by taking the number of injections (regardless of the actual dose administered) divided by the total number of injections expected to be administered $\times 100$. Insulin glargine compliance will be calculated by taking the total number of injections expected minus the total number of injections missed (regardless of the actual dose administered) divided by the total number of injections expected to be administered $\times 100$. Overall treatment compliance will be summarized descriptively by treatment using the mITT population.

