5.4. Screen Failures

A screen failure occurs when a participant who consents to participate in the clinical study is not subsequently randomly assigned to study drug. A minimal set of screen failure information is required to ensure transparent reporting of screen failure participants to meet the Consolidated Standards of Reporting Trials (CONSORT) publishing requirements and to respond to queries from regulatory authorities. Minimal information includes demography, screen failure details, eligibility criteria, and any serious adverse event (SAE).

Individuals who do not meet the criteria for participation in this study (screen failure) must not be rescreened.

5.5. Criteria for Temporarily Delaying Enrollment/Randomization/Administration of Study Intervention of a Participant

Not applicable.

6. Study Intervention(s) and Concomitant Therapy

Study intervention is defined as the study drug (tirzepatide 3 doses or placebo) intended to be administered to a study participant according to the study protocol.

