6.1. Study Intervention(s) Administered

Assignment to tirzepatide (3 doses) or placebo will occur at randomization. Beginning at randomization, all participants will receive study drug according to the randomized treatment group for the duration of the 40-week treatment period. Following randomization, the participant will inject the first dose of study drug/placebo at the study site. The date and time of all doses of study drug should be recorded on the eCRF.

This table lists the interventions used in this clinical study.

Group Name	Tirzepatide 5 mg	Tirzepatide 10 mg	Tirzepatide 15 mg	Placebo	Concomitant background insulin for all treatment arms
Intervention Name	Tirzepatide 5 mg	Tirzepatide 10 mg	Tirzepatide 15 mg	Placebo	Insulin Glargine U100
Dosage Level(s)	5 mg QW	10 mg QW	15 mg QW	NA	Titrated
Route of Administration	SC				
Frequency of Administration	QW				QD
Use	Experimental intervention			comparator	Concomitant background insulin
Sourcing	Provided centrally by the Sponsor and dispensed via IWRS				
Packaging and Labeling	Will be provided in autoinjectors (single-dose pens) and packaged in cartons to be dispensed. Clinical study materials will be labeled according to country regulatory requirements.				

Abbreviations: IWRS= interactive web-response system, QD= once daily, QW=once weekly, SC=subcutaneous.

[figure not shown]

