6.4. Study Intervention Compliance

Study drug compliance will be determined by the following:

- Study drug administration data will be recorded by the participant and reviewed by the investigator at each study visit.
- The participants will be instructed to return any unused study drug and/or empty cartons at the next visit to the study site for the purpose of performing drug accountability.

In the 3 tirzepatide treatment groups, as well as the placebo group, treatment compliance is defined as taking at least 75% of the required doses of study drug. Similarly, a participant will be considered noncompliant if he or she is judged by the investigator to have intentionally or repeatedly taken more than the prescribed amount of medication.

In addition to the assessment of a participant's compliance with the study drug administration, other aspects of compliance with the study treatments will be assessed at each visit based on the participant's adherence to the visit schedule, completion of study diaries, the results of home BG monitoring, and any other parameters the investigator considers necessary.

Participants considered not to be compliant with their medication and/or the study procedures will receive additional training and instruction, as required, and will be reminded of the importance of complying with the protocol.

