9.3.2.4. Treatment Compliance

Of the participants in the mITT population, frequency counts and percentages of participants prematurely discontinuing study drug, including the reason for premature discontinuation, will be presented by treatment group. A Kaplan-Meier analysis of time from randomization to premature study drug discontinuation by treatment group will be provided.

Treatment compliance is defined as taking at least 75% of required injections of study drug. Frequency counts and percentages of participants compliant to study drug will be summarized by treatment arm using the mITT population.

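### SAP 6.2 lets background glargine count toward treatment compliance, so the descriptive compliance table could overstate adherence to study drug as the protocol defines it

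*SAP*

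**What the plan says.** Protocol 6.4, for the three tirzepatide arms and placebo: "treatment compliance is defined as taking at least 75% of the required doses of study drug". Protocol 9.3.2.4 repeats the rule in the statistical section, "Treatment compliance is defined as taking at least 75% of required injections of study drug", and specifies the output: "Frequency counts and percentages of participants compliant to study drug will be summarized by treatment arm using the mITT population". The opening of protocol Section 6 identifies study drug as tirzepatide or placebo. The intervention table in protocol 6.1 lists insulin glargine as "Concomitant background insulin for all treatment arms".

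SAP 6.2 uses a different rule for overall compliance: "taking at least 75% of the scheduled study drug or insulin glargine injections". It then gives two percentage formulas, one for study drug and one for glargine, each divided by the injections expected. The output it names is a single one: "Overall treatment compliance will be summarized descriptively by treatment using the mITT population". It mentions no separate summary of study drug compliance. SAP 4.10, the section for changes to protocol-planned analyses, is marked not applicable.

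**The concern.** The protocol rule has no glargine component and the SAP rule does. Every arm takes glargine daily as background treatment, and participants who stop or skip study drug remain in the study. If meeting the threshold on glargine is enough, the compliance figure no longer describes exposure to tirzepatide or placebo, which is what the protocol said it would describe.

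At stake is the accuracy of one reported figure. The compliance table is the arm-level summary that would show doses missed by participants who stay on study drug. If glargine use can make up for those misses, the table may show better study drug adherence than occurred.

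**Working it through.** The plan states no compliance rate, so there is no figure to reproduce. The check classifies example participants under each rule.

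**Inputs**
- Treatment period of 40 weeks (protocol 4.1) with weekly study drug: 40 × 1 = 40 expected injections; 75% is 30.
- Glargine once daily (protocol 6.1.3): 40 × 7 = 280 expected injections; 75% is 210.
- Pooled: 40 + 280 = 320; 75% is 240.
- Assumption: expected injections run over the full 40 weeks for both products.

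**Formulas (SAP 6.2)**
- Study drug % = injections taken / injections expected × 100.
- Glargine % = (expected − missed) / expected × 100.

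**Classification**

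| Study drug | Glargine | Protocol rule | SAP, either component | SAP, pooled | SAP, each component separately |
|---|---|---|---|---|---|
| 24/40 = 60% | 280/280 = 100% | Non-compliant | Compliant | 304/320 = 95%, compliant | Non-compliant on study drug |
| 24/40 = 60% | 210/280 = 75% | Non-compliant | Compliant | 234/320 = 73.1%, non-compliant | Non-compliant on study drug |
| 4/40 = 10% | 280/280 = 100% | Non-compliant | Compliant | 284/320 = 88.8%, compliant | Non-compliant on study drug |
| 30/40 = 75% | 280/280 = 100% | Compliant | Compliant | 310/320 = 96.9%, compliant | Compliant on both |

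The first row is the robust case. That participant never stops study drug but misses 40 − 24 = 16 doses along the way, so the result does not depend on how injections are counted after discontinuation. The third row, an early stopper, does depend on it.

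**Bound for participants who stop.** Protocol 9.5 and SAP Section 5 assume that no more than 25% per arm start rescue or stop study drug, and 64 are planned per arm: 0.25 × 64 = 16. Suppose all 16 stop before their 30th dose, all keep at least 75% of glargine, 40 doses remain expected, and everyone else is compliant. The protocol rule then gives 48/64 = 75% and the literal SAP rule 64/64 = 100%. The documents give no figure for intermittent missed doses.

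**Would other outputs show the first-row participant?** Duration on study treatment in SAP 4.6.1 runs from first to last dose plus 7 days, so skipped doses in between do not shorten it. The listing of participants who restart after missing three or more consecutive doses is optional. Discontinuation tables do not apply to someone who has not discontinued.

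**The case against.** SAP 6.2 never says that meeting either component is sufficient. The two separate formulas follow directly after the definition, so one 75% threshold applied to each product is a plausible reading, and on that reading no one is misclassified. The commitment in protocol 9.3.2.4 has not been withdrawn, and both documents allow a change of method to be described in the clinical study report instead of the SAP.

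Exposure is also visible elsewhere. SAP 4.2, 4.6.1 and 4.6.2.4 report study drug discontinuation by arm, with reasons and time-to-event analyses. SAP 4.6.3.12 covers gastrointestinal events directly.

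The bound is weak as a forecast. The 25% is a planning ceiling that includes rescue starters, and rescue is added to randomized treatment (protocol 8.3.4.2), so those participants need not have missed any study drug. Anyone who stops after 30 of 40 doses passes both rules. Glargine itself may be stopped for repeated hypoglycemia (protocol 6.5.2). Neither document says whether expected injections continue after permanent discontinuation; if they end there, an early stopper can be compliant under the protocol rule too.

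Most of this stands, and it limits the consequence. It does not remove the mismatch. The per-component reading is possible but not written, and it does not explain how two thresholds produce the single overall figure that SAP 6.2 names for summary. The discontinuation outputs do not capture participants who remain on study drug and miss doses.

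**Conclusion.** The definitions conflict and the SAP does not declare the difference. Under the literal or pooled reading, a participant with more than 25% of study drug doses missed can be reported as compliant, so the table could overstate study drug adherence. By how much cannot be determined from the documents; 100% against 75% is the ceiling for the stoppers in the planning allowance, under the assumptions shown, and not an expected result.

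A reader might infer more than this:
- That anyone who stops study drug but keeps injecting glargine will certainly be reported as compliant. This depends on the reading of SAP 6.2; and if expected doses end at stopping, such a participant may pass the protocol rule as well.
- That the rate will rise toward 100% in every arm. No document gives the rates needed to say so.
- That the gastrointestinal tolerability picture or the efficacy comparison is distorted. Gastrointestinal events and discontinuations have their own analyses, and no analysis set, estimand or test in either document uses the 75% rule.

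The effect is confined to one descriptive mITT table and mainly concerns intermittent non-adherence. It should still be corrected, because a stated rule can yield a reported figure that differs from the one the protocol promised.

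**What to change.** In SAP 6.2:
- Define treatment compliance as at least 75% of scheduled study drug injections, as in protocol 9.3.2.4, and summarize it by arm in the mITT population.
- Report glargine compliance as a separate line.
- State whether expected injections continue to be counted after permanent discontinuation.

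If the inclusion of glargine was intended, declare and justify it in SAP 4.10.

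The cost is SAP wording and one table shell, with no new data. The reported compliance rate may be less favourable.

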6.3. Concomitant Therapy

The prespecified concomitant medications of interest will be summarized by treatment at randomization. Additionally, medications of interest initiated after randomization and change to medications of interest used at randomization will be summarized. The concomitant therapies will be mapped using the World Health Organization Drug dictionary in the clinical trial database.

The concomitant medications of interest include the following groups of medication:

- baseline antihyperglycemic medication
- baseline antihypertensive therapy
- baseline lipid lowering therapy
- changes to baseline medication in Study Period
 - antihypertensive therapy
 - lipid lowering therapy
- rescue therapy due to severe persistent hyperglycemia
- initiation of antihyperglycemic medication after study treatment discontinuation
- initiation of the following medications in Study Period:
 - antidiarrheal medication
 - antiemetic medication

6.4. Clinical Trial Registry

Additional analyses will be performed for the purpose of fulfilling the Clinical Trial Registry (CTR) requirements.

Analyses provided for the CTR requirements include the following:

- Summary of adverse events, provided as a dataset which will be converted to an XML file. Both Serious Adverse Events and ‘Other’ Non-Serious Adverse Events are summarized: by treatment group, by MedDRA preferred term.
 - An adverse event is considered ‘Serious’ whether or not it is a treatment emergent adverse event (TEAE).
 - An adverse event is considered in the ‘Other’ category if it is both a TEAE and is not serious. For each Serious AE and ‘Other’ AE, for each term and treatment group, the following are provided:
 - the number of participants at risk of an event
 - the number of participants who experienced each event term
 - the number of events experienced.
- For each Serious AE, these additional terms are provided for EudraCT:
 - the total number of occurrences causally related to treatment
 - the total number of deaths
 - the total number of deaths causally related to treatment.
- Consistent with www.ClinicalTrials.gov requirements, ‘Other’ AEs that occur in fewer than 5% of patients/subjects in every treatment group may be excluded if a 5% threshold is chosen. Allowable thresholds include 0% (all events), 1%, 2%, 3%, 4% and 5%.
- AE reporting is consistent with other document disclosures for example, the CSR, manuscripts, and so forth.

Demographic table including the following age ranges required by EudraCT: in utero, preterm newborn infants (gestational age <37 weeks), newborns (0-27 days), infants and toddlers (28 days – 23 months), children (2-11 years), adolescents (12-17 years), adults (18-64 years), 65-85 years, and 85 years and over.

7. Appendices

7.1. Appendix 1. SAS Code for Multiple Imputation

```
*retrieved dropout imputation*;
*ret_flg is a flag variable for subjects that are retrieved dropouts*;
proc mi data=&dataset_in. seed=&seed. out=&dataset_out. nimpute=&n_impute. ;
by trtpn;
class ret_flg;
monotone reg(chg/details);
mnar model (chg/modelobs=(ret_flg='Y'));
var base chg;
run;

*placebo imputation*;
*replace 'placebo' with the assigned value for the placebo group*;
proc mi data=&dataset_in. seed=&seed. out=&dataset_out_2. nimpute=&n_impute. ;
class trtpn;
monotone reg(chg/details);
mnar model (chg/modelobs=(trtpn='placebo'));
var base chg;
run;
```

